8.7	Drug Safety Specialist updated	Assure correct reporting procedures to pharmacovigilance.

SYNOPSIS

Sponsor	IVIEW Therapeutics, Inc.
Study Title	Phase 1/2a, Proof-of-Concept, Multicenter, Parallel, Vehicle-Controlled, Double-Masked, Randomized Study Evaluating the Safety, Tolerability, and Efficacy of IVW-1001 Ophthalmic Eyelid Wipe in Subjects With Dry Eye Disease
Protocol Number	IVW-1001-CS-101
Indication	Dry eye disease (DED)
Sites	Up to approximately 10 sites throughout the United States (US)
Phase of Development	Phase 1/2a
Objectives	The objectives of this study are to assess the safety and efficacy of IVW-1001 Ophthalmic Eyelid Wipe in subjects with DED.
Primary Safety Outcome Measures	
The primary safety measures are:
 
• Mean change from baseline in:
○ Best-corrected visual acuity (BCVA)○ Slit lamp biomicroscopy○ Intraocular pressure (IOP)○ Dilated ophthalmoscopy• Visual analog scale (VAS) of investigational product (IP) tolerability• Adverse events (AEs)
Primary Efficacy Outcome Measures	
The primary efficacy endpoint is:
 
• Mean change from baseline at Day 29 (Week 4/End of Study) in the study eye in unanesthetized Schirmer's test
Exploratory Efficacy Outcome Measures	
The exploratory efficacy endpoints are:
 
• Mean change from baseline in:
○ Unanesthetized Schirmer's test (Weeks 1, 2, and 3)○ VAS of IP comfort (ASHRAE 7-Point Scale)○ VAS of Eye Dryness Score (EDS)○ VAS of Ocular Discomfort Score (ODS)○ Symptom Assessment in Dry Eye (SANDE) questionnaire○ Corneal fluorescein staining (inferior zone)○ Corneal fluorescein staining (total of all zones)○ Anesthetized Schirmer's test• Proportion of subjects ≥ 10 mm increase in unanesthetized Schirmer's test score

	
• Proportion of subjects ≥ 10 mm increase in anesthetized Schirmer's test score
Study Design	This is a randomized (1:1:1), multicenter, parallel, vehicle-controlled, double-masked study to evaluate the safety, tolerability, and efficacy of IVW-1001 Ophthalmic Eyelid Wipes in subjects with DED. Treatments will be IVW-1001 Ophthalmic Eyelid Wipe 0.2% (high dose), IVW-1001 0.1% (low dose), or IVW-1001 Ophthalmic Eyelid Wipe Placebo (vehicle). Subjects will participate in a 7-day, single-masked vehicle run-in period followed by a 28-day, double-masked treatment period.
Inclusion Criteria	
Each subject must meet the following criteria to be randomized in this study.
 
1. Subjects of any gender at least 18 years of age at the Screening Visit2. Able to voluntarily provide written informed consent to participate in the study3. Able and willing to comply with all study procedures and restrictions, follow study instructions, and complete required study visits4. Self-reported diagnosis of DED in one or both eyes5. BCVA $+0.70$ logMAR (Snellen equivalent 20/100) or better in each eye at the Screening Visit6. For women of childbearing potential, confirmed negative pregnancy test at the Screening Visit and the Baseline Visit, not nursing a child, and willing to comply with one of the acceptable methods of birth control described in the protocol7. History (by subject recollection) of artificial tear use within 30 days prior to the Screening Visit8. Willingness to suspend use of artificial tears during study participation9. Willingness to suspend use of contact lenses during study participation10. Able to demonstrate adequate self-administration of the run-in eyelid wipe to upper eyelid at the Screening Visit11. Unanesthetized Schirmer's test score between 5 and 10 mm (inclusive) in at least 1 eye (same eye) at the Screening Visit and the Baseline Visit12. Total corneal fluorescein staining score between 5 and 13, representing the sum of scores of all 5 regions (inferior, superior, nasal, temporal, and central) using the National Eye Institute (NEI) grading system (0-4 scale) in at least one eye at the Screening Visit and the Baseline Visit13. EDS VAS ≥ 40 at the Screening Visit and the Baseline Visit, with ≤ 20 units of improvement from the Screening Visit to the Baseline Visit

Exclusion Criteria	
Subjects who meet any of the following criteria will be excluded from randomization.
 
Ocular history – medical
 
1. Corneal fluorescein staining score of 4 in either eye in any zone using the NEI grading system at either the Screening Visit or the Baseline Visit2. IOP ≥ 23 mmHg in either eye at either the Screening Visit or the Baseline Visit3. History of glaucoma or ocular hypertension in either eye requiring past or current medical or surgical intervention4. History of contact or scleral lens use in either eye within 30 days prior to the Screening Visit or anticipated use during the study5. Subjects with ocular inflammatory conditions (eg, conjunctivitis, keratitis, severe anterior blepharitis, etc.) not related to DED at the Screening Visit or the Baseline Visit6. Suspected ocular fungal, viral, or bacterial infection at the Screening Visit or the Baseline Visit. Note: Mild blepharitis is permitted7. Presence of trigger factors that, in the opinion of the Investigator, may confound the study data, including but not limited to conjunctivochalasis, allergic conjunctivitis, trichiasis, epithelial basement membrane dystrophy, infectious keratitis, or conjunctivitis 
Ocular history – surgical/procedural
 
8. Routine use (as defined by the Investigator) of lid hygiene products (warm compresses, medicinal eyelid wipes, eyelid scrubs, mechanical eyelid cleaning therapy) within 30 days prior to the Screening Visit or inability or unwillingness to withhold use during study participation. Note: Makeup removal products are permitted9. Treatments for meibomian gland dysfunction (MGD) within 30 days prior to the Screening Visit or anticipated use during the study, including but not limited to thermal pulsation (Lipiflow®, iLux®), debridement of lid margin (BlephEx®), moisture chamber goggles, or thermal application (MiBoFlo Thermoflo®, TearCare®)10. Cauterization of the punctum within 90 days prior to the Screening Visit or anticipated during study participation11. Non-dissolvable punctal plugs inserted within 90 days prior to the Screening Visit or, in the opinion of the Investigator, considered unstable and likely to become displaced12. Long-term dissolvable punctal plugs inserted within 90 days prior to the Screening Visit 
Prior medications and therapies in either eye

---------------------------	---

	
13. Use of artificial tears within 2 hours prior to the Screening Visit or anticipated use during study participation14. Use of the following therapies within 30 days prior to the Screening Visit or anticipated use during study participation:
a. Topical cyclosporine (Restasis[®], Cequa[®], or VevyeTM [previously known as CyclASol[®]])b. Topical brimonidine (prescription or over-the-counter [OTC])c. Topical lifitegrast (Xiidra[®])d. Topical perfluorohexyloctane (MieboTM)e. Topical ocular corticosteroids or nonsteroidal anti-inflammatory drugs (NSAIDs)f. Any other prescription or OTC topical eye lid (including wipes) or ocular medications for DED and/or MGD or any other indication that, in the opinion of the Investigator, might interfere with study assessments
	
Prior non-ocular medications
 
15. Use of medications for the treatment of DED and/or MGD such as oral tetracyclines, oral tetracycline derivatives, oral or topical macrolides (such as azithromycin), and oral retinoids (Note: Current or past isotretinoin use is exclusionary) within 30 days prior to the Screening Visit or anticipated use during the study16. Initiation, discontinuation, or change in dosing of any systemic corticosteroid within 30 days prior to the Screening Visit or an anticipated change in dosage during the study
a. Topical non-ocular dermal corticosteroids may be used up to 3 times per week in no more than 3 locations simultaneously. No periocular use is permittedb. Intranasal corticosteroids are permitted with a stable dosing history during the 30 days prior to the Screening Visit and without an anticipated change in dosage during the study17. Use of NSAIDs, including aspirin, unless:
a. Used with a stable dosing history during the 30 days prior to the Screening Visit without an anticipated change in dosage during the studyb. Used as needed (PRN) no more than 3 times weeklyc. Note: Acetaminophen has no restrictions on its use18. Initiation, discontinuation, or change in dose of a systemic medication (oral or topical) known to cause ocular drying (eg, antihistamines or tricyclic antidepressants) within 30 days prior to the Screening Visit or an anticipated change in dosage during the study. Note: These agents are permitted when used PRN to treat insomnia19. Initiation, discontinuation, or change in dose of any systemic immunomodulator (eg, hydroxychloroquine, methotrexate,

	
cyclosporine) within 30 days prior to the Screening Visit or an anticipated change during the study. Note: Treatment with vaccines is allowed during study participation
 
20. Use of Tyrvaya® (varenicline solution, nasal spray) within 30 days prior to the Screening Visit or anticipated use during the study
 
21. Any prior use of isotretinoin (Accutane®) or anticipated use during the study
 
Systemic conditions or procedures
 
22. History of allergic conjunctivitis requiring use of prescription or OTC topical antihistamine therapy within the last 14 days
 
23. History or presence of significant (in the opinion of the Investigator) systemic (eg, cardiovascular, pulmonary, hepatic, renal, hematologic, immunologic) conditions
 
24. Any significant physical or mental condition that, in the opinion of the Investigator, could interfere with study participation
 
25. Any planned surgical procedure that could interfere with study participation
 
Lifestyle related
 
26. Participation in any interventional investigational drug or device trial within 30 days prior to the Screening Visit
 
27. Employed by study site, or an immediate family member of site staff, and directly involved in clinical activities related to this study

Study Population	The subject population to be studied is comprised of subjects with DED confirmed at the Screening Visit who, after a 7-day, single (subject)-masked vehicle run-in period, continue to meet eligibility requirements at the Baseline Visit.
Investigational Product, Dose, and Mode of Administration	
The IPs to be administered in this study are IVW-1001 Ophthalmic Eyelid Wipe 0.1%, IVW-1001 Ophthalmic Eyelid Wipe 0.2%, and IVW-1001 Ophthalmic Eyelid Wipe Placebo (vehicle) for eyelid application.
 
Each unit dose will contain 2 polyester wipes saturated with a solution containing active ingredient (except vehicle, which contains no active ingredient), sodium hyaluronate, mannitol, and water for injection in a clear glass bottle.
 
One unique wipe will be used for the application to the upper eyelid of each eye, moving in a nasal to temporal direction while applying modest pressure.

Duration of Study	This study has a duration of approximately 5 weeks, with a 7-day run-in period and a 28-day treatment period.
Number of Subjects	Approximately 150 subjects are targeted for enrollment.

ICH	International Council for Harmonisation of Technical Requirements for Registration of Pharmaceuticals for Human Use
IOP	intraocular pressure
IP	investigational product
IRB	Institutional Review Board
IWRS	Interactive Web Response System
MedDRA	Medical Dictionary for Regulatory Activities
MGD	meibomian gland dysfunction
mITT	Modified Intention-to-Treat
NEI	National Eye Institute
NSAID	nonsteroidal anti-inflammatory drug
ODS	Ocular Discomfort Score
OTC	over-the-counter
OU	oculus uterque; both eyes
PP	Per Protocol
PRN	pro re nata; as needed
SAE	serious adverse event
SANDE	Symptom Assessment in Dry Eye
SD	standard deviation
US	United States
VA	visual acuity
VAS	visual analog scale
WOCBP	women of childbearing potential

1 INTRODUCTION

In 2017, the Tear Film and Ocular Surface Society Dry Eye Workshop II (TFOS-DEWS II) defined dry eye disease (DED) as “...a multifactorial disease of the ocular surface characterized by a loss of homeostasis of the tear film, and accompanied by ocular symptoms, in which tear film instability and hyperosmolarity, ocular surface inflammation and damage, and neurosensory abnormalities play etiological roles” ([Craig 2017](#)). TFOS-DEWS II goes on to state, “The management of DED is complicated, due to its multifactorial etiology...The ultimate aim of DED management is to restore the homeostasis of the ocular surface and tear film, through breaking the vicious cycle of the disease.” A wide range of treatments are available based upon the nature and severity of the patient’s DED. Management of DED generally begins with conventional, low-risk self-administered therapies, including over-the-counter (OTC) lubricant eye drops, and progresses to more advanced therapies as severity increases ([Craig 2017](#)). However, many patients are still not optimally treated despite the availability of numerous approved therapeutic products.

As recently reviewed, researchers have discovered that thermal changes at the ocular surface activate cool neurons and may affect surface wetness ([Yang 2018](#)). TRPM8 receptors, which are located on the cornea and eyelid at the base of eyelash follicles ([Yang 2017](#)), appear to be first activated after evaporation of the tear film ([Belmonte 2017](#)); these may be associated with the detection of “dryness” on the eye surface ([Parra 2014](#); [Quallo 2015](#)). TRPM8 may also be a direct stimulator of tear secretion from the lacrimal gland ([Parra 2010](#)).

In order to test this hypothesis, a TRPM8 agonist was synthesized (IVW-1001; cryosim-3; C3; 1-diisopropyl-phosphinoyl-nona; [Yang 2017](#)). In nonclinical models of mouse DED, single topical ocular doses of C3 0.2% showed activity ([Yang 2017](#)). IVW-1001 0.2% singly applied ocular topically increased tear secretion in healthy rabbits.

In clinical C3 studies conducted in Korea in subjects with DED, 60 subjects (n=30 per group) participated in a single-dose study, and 40 subjects (n=20 per group) completed a 2-week, repeat-dose study. Cryosim-3 or vehicle (water) was applied with a cotton gauze pad to upper eyelids of subjects with DED (n=30). Cooling sensation, tear film break-up time (TBUT), basal tear secretion, and corneal staining were evaluated. Cryosim-3 was then applied 4 times daily (QID) for 2 weeks to subjects using a pre-loaded single-unit applicator containing C3 2 mg/mL (0.2%) in water (n=20) or water only. After 2 weeks of QID dosing with C3 0.2% as an eyelid wipe, subjects experienced improved signs and symptoms relative to the control (water) group ([Yang 2017](#)). An open-label, non-comparative pilot study was also conducted in Korea in 20 subjects with neuropathic ocular pain ([Yoon 2021](#)). After 1 month of treatment with C3 0.2% eyelid wipes, subjects experienced improvement in ocular pain symptoms, quality of life, and Schirmer’s test scores.

In this protocol, IVW-1001 Ophthalmic Eyelid Wipe is being evaluated for the treatment of subjects with DED. The final drug product is a single-use, preservative-free, sterile eyelid wipe that is saturated with either C3 0.1% ophthalmic solution, C3 0.2% ophthalmic solution, or a vehicle ophthalmic solution on a polyester cloth. Two wipes (1 for each eye) are sealed into a glass vial. Also provided are tweezers to extract the wipe from the vial. IVW-1001 is a new drug substance, and there is no previous human experience in the United States (US).

1.1 Indication

In this clinical trial, the population to be studied is subjects with DED confirmed by Screening Visit 1 assessments.

1.2 Investigational Products

IVW-1001 Ophthalmic Eyelid Wipe is a single-use, preservative-free, sterile eyelid wipe that is saturated with C3 0.1% ophthalmic solution, C3 0.2% ophthalmic solution, or a vehicle ophthalmic solution on a polyester cloth. Two wipes (1 for each eye) are sealed into a glass vial. Also provided are tweezers to extract the wipe from the vial.

1.3 Nonclinical Experience

Please see the Investigator's Brochure for this information.

1.4 Clinical Experience

IVW-1001 is a new drug substance, and there is no previous human experience in the US.

1.5 Risks and Benefits

Based upon previous human evaluation and this class of compounds, the primary potential risk of IVW-1001 is ocular discomfort. The potential benefits are improvements in signs and symptoms of ocular surface disease.

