2.2 Measures

2.2.1 Safety

The primary safety measures are:

- Mean change from baseline in:
 - Best-corrected visual acuity (BCVA)
 - Slit lamp biomicroscopy
 - Intraocular pressure (IOP)
 - Dilated ophthalmoscopy
- Visual analog scale (VAS) of investigational product (IP) tolerability
- Adverse events (AEs)

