7.4.6 Investigational Product Tolerability Visual Analog Scale

Investigational product tolerability will be measured on a scale ranging from 0 (no discomfort) to 100 (severe discomfort; [Appendix 2](#)). Study staff will measure and record the VAS scores. Score cards will be retained for measurement confirmation.

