9.5 Safety Analyses

The assessment of safety will be based on the summaries of ocular and non-ocular AEs and ophthalmic examination findings. Adverse events reported during the study will have their verbatim

terms mapped to the corresponding thesaurus terms from the most current version of the Medical Dictionary for Regulatory Activities (MedDRA) coding dictionary. All summaries of AEs will be based on the assigned MedDRA preferred term and system organ class, and summaries will be given for each of the randomized treatment groups.

Separate summaries of AEs related to treatment (as reported by the Investigator) and by severity will be prepared. The number of SAEs will also be presented, and events leading to discontinuation from the study will be listed and tabulated.

Other safety assessments will be presented descriptively (absolute values and changes from baseline). These will include BCVA, IOP, slit lamp biomicroscopy, dilated ophthalmoscopy, and tolerability assessment. Continuous variables will be summarized by descriptive statistics, and categorical variables will be summarized using the count and percentage of subjects in each category. Shift tables will be prepared by treatment group showing all categorical changes from baseline to each study visit.

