3.3. Multiplicity Adjustment

Due to the early phase of the study and because the primary objective is the assessment of safety, there will be no adjustments for multiplicity in the testing of the efficacy endpoints.

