7.2. Primary Safety Endpoint Assessments and Analysis

The primary objectives for this study are to investigate the safety and tolerability of the IVW-1001 Ophthalmic Wipe based on the following safety endpoints:

- CFB in BCVA, slit lamp biomicroscopy, IOP and dilated ophthalmoscopy
- VAS of IP tolerability
- Adverse Events

Safety analyses will be performed on all subjects who received at least 1 dose of IP (SAF Population). The assessment of safety will be based on the summary of ocular and non-ocular AEs and ophthalmic/medical exams (BCVA, slit lamp biomicroscopy, IOP, dilated ophthalmoscopy and tolerability assessment). Summaries will be provided for each treatment arm, and for the ophthalmic exams, separately for SE and FE.

Safety variables will be presented descriptively. Continuous variables will be summarized by descriptive statistics (absolute values and changes from baseline), and categorical variables will be summarized using the count and percentage of subjects in each category. For the biomicroscopy and ophthalmoscopy variables, shift tables will be prepared by treatment arm showing all categorical changes (e.g., normal to abnormal) from baseline to each study visit.

All data will be presented in data listings.

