7.2.3.5. VAS of IP Tolerability

A VAS evaluation of the IP tolerability will be performed at all visits and the Day 1 value will be used as the baseline value. Subjects will grade the tolerability of the IP after administration on a scale of 0 (no discomfort) to 100 (severe discomfort) by placing a vertical mark on the horizontal line shown below. The mark will be measured and recorded.

The VAS will be measured at all visits and the Day 1 value will be used as the baseline value. The observed value and change from baseline for each subsequent post-baseline visit will be summarized descriptively by visit and treatment arm.

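### The tolerability VAS, a primary safety measure of the protocol's named primary risk, has no planned dose-minus-vehicle estimate with an interval, and its Day 1 baseline is already post-dose.

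*Protocol*

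**What the plan says.** Protocol 1.5 names one main hazard: "the primary potential risk of IVW-1001 is ocular discomfort". Protocol 2.2.1 lists "Visual analog scale (VAS) of investigational product (IP) tolerability" as a primary safety measure, and Protocol 7.4.6 defines it as a 0-100 score on which higher means more discomfort. The SAP gives safety priority; section 3.3 drops multiplicity control partly "because the primary objective is the assessment of safety".

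The planned analysis is descriptive in both documents. Protocol 9.5 says "Other safety assessments will be presented descriptively (absolute values and changes from baseline" and includes the tolerability assessment in that group. SAP 7.2 says "Safety variables will be presented descriptively". SAP 7.2.3.5 has the observed tolerability score and its change from baseline "summarized descriptively by visit and treatment arm", with Day 1 as baseline.

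SAP 7.1 names the contrasts of 0.2% and 0.1% with Vehicle for the primary and exploratory efficacy endpoints. It also has a general clause allowing comparative analysis of continuous variables where appropriate, which does not mention tolerability. The exploratory change-from-baseline endpoints, including the ODS and ASHRAE comfort VAS, go through the mixed model of SAP 7.3.3, which reports least-squares differences with confidence intervals.

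**The concern.** The vehicle wipe and the act of wiping can themselves cause discomfort, so only the difference from vehicle speaks to the drug. Three columns of means do not show directly how precisely that difference is known for either concentration. The score that measures the named risk gets less analysis than the exploratory efficacy scores.

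The baseline makes this worse. Half of the planned tolerability display is change from Day 1. If the Day 1 score already contains the effect of the assigned product, that half can show no difference between arms even when one dose is consistently less comfortable than vehicle. What is at stake is the tolerability information that the study is meant to supply on two concentrations.

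**Working it through.** **1. No plan figure to reproduce.** Neither document states a sample size, power or precision for the tolerability VAS. The stated power of at least 80% with 46 per group concerns Schirmer's test. It reproduces by the normal approximation (82.2% with the Protocol inputs of 3.3 mm, SD 5.0 and alpha 0.025; 82.1% with the SAP inputs of 3.0 mm, SD 5.0 and alpha 0.05), but it does not bear on this point.

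**2. Do the modelled symptom scales cover the gap?**
- *ODS VAS.* Protocol 7.5.2 to 7.5.4 place it before the in-office dose. Subjects do not dose at home on the morning of Visits 3-6 (Protocol 3.7). Appendix 5 asks about dry eye symptoms at that moment. It therefore does not record discomfort on application.
- *ASHRAE comfort VAS.* It runs from -3 to +3, is classed as exploratory efficacy, and is taken before dosing and at up to four times after (Protocol 7.4.7). SAP 7.4.1.1 does not say which time enters the model.
- *Tolerability VAS.* It is taken 5 to 15 minutes after the wipe at every visit (SAP Table 1, footnote m). Of the three, it is the only one that scores post-application discomfort from 0 to 100.

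**3. What change from Day 1 estimates.** Protocol 7.5.2 puts randomization and the in-office dose before the Day 1 tolerability score. Let the dose-minus-vehicle excess be d1 on Day 1 and dv at a later visit v.
- Expected difference in change from Day 1 = dv - d1.
- If the excess is constant (dv = d1), this is 0 whatever its size.
- At Screening every subject has received vehicle, so the expected excess there is 0. The expected difference in change from Screening is dv - 0 = dv.
- The difference in observed scores at visit v is also dv, and on Day 1 it is d1.

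**4. Precision available from the planned sample.** For one dose against vehicle at one visit:

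half-width = t(0.975, 2n-2) x SD x sqrt(2/n)

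- n = 50 per arm (randomized): multiplier 0.397.
- n = 46 per arm (expected completers): multiplier 0.414.

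| Assumed SD (units) | Half-width, n = 50 | Half-width, n = 46 |
|---|---|---|
| 15 | 6.0 | 6.2 |
| 20 | 7.9 | 8.3 |
| 25 | 9.9 | 10.4 |
| 30 | 11.9 | 12.4 |

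The SDs are assumptions. The table shows the precision of a crude two-arm comparison. Any gain from the repeated-measures model or the Screening covariate is not included.

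**The case against.** The strongest defence is that this is ordinary early-phase practice. The trial is Phase 1/2a and states no tolerability hypothesis, margin or precision target. The other primary safety measures are also handled descriptively. That stands, and it is why intervals without tests are enough.

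Four stronger readings are tempting, and the documents do not support them.
- A reader might infer that discomfort relative to vehicle is never estimated. SAP 7.4.1.1 and 7.4.2 plan modelled differences from vehicle for the ODS and comfort VAS. Only the tolerability VAS lacks one.
- A reader might infer that the SAP weakened what the protocol promised. Protocol 9.5 is already descriptive for tolerability, so the SAP follows it.
- A reader might infer that SAP 7.1 forbids a tolerability comparison. Its list of comparisons is not worded as exclusive, and the clause on continuous variables leaves discretion. The accurate statement is that nothing commits to the comparison.
- A reader might infer that the trial could not answer its tolerability question. SAP 7.1 requires N, mean and SD, and observed values are tabulated by visit and arm, so anyone could work out a crude difference and interval. What is missing is a prespecified, reported estimate.

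The defence does not answer the baseline problem. A post-dose Day 1 baseline is a flaw in a descriptive table as much as in a model.

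**Conclusion.** The concern holds in a limited form: a gap in the planned analysis and an unsuitable baseline, not a contradiction between the documents or a calculation error. The measure of the named primary risk has no prespecified contrast with vehicle, and the modelled ODS and comfort scales do not stand in for it. The planned change-from-baseline summary can cancel a constant excess completely; the table of observed values is unaffected.

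The achievable half-width is about 6 to 12 units on the 100-unit scale at 50 per arm. This rests wholly on assumed SDs of 15 to 30, on approximately normal scores and on a comparison at a single visit. It describes the precision available, not a bias. No claim that a relevant excess has been ruled out can be made without a margin, and the documents give none. The change is worth making because the data are already collected.

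**What to change.** Amend SAP 7.2.3.5 along these lines: *In the SAF population, the observed post-dose tolerability VAS at Visits 2-6 will be analysed with a repeated-measures model with Treatment, Visit and Treatment\*Visit as fixed effects and the Screening score (run-in vehicle) as covariate. The difference of each dose from Vehicle will be reported at each visit with a 95% confidence interval and no hypothesis test.*

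Keep the descriptive tables of observed values. For change from baseline, either use the Screening score as baseline or drop the summary. State the baseline change and the added model in SAP 7.7, since Protocol 9.5 foresaw descriptive presentation only.

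The cost is one further model specification and ten intervals (2 doses x 5 visits). It is not a plain rerun of the SAP 7.3.3 model, which uses change from baseline, the Day 1 covariate and the mITT population. It needs no new subjects, visits or assessments, and with no tests it adds nothing to the multiplicity question.
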